HCQ has an established safety profile that permits chronic treatment. The major adverse effect is retinal toxicity, described in long-term use with both chloroquine and HCQ.[21, 22] This effect is related to the cumulative dose of either agent. Clear guidelines have been developed for ocular screening and follow-up of patients taking these agents, and were recently updated.[23] There are no reports of an interaction between chloroquine/HCQ retinal toxicity and diabetic retinopathy. Other adverse effects include neuropathy and myopathy, which are described in long-term users of the drugs and are considered rare.

The primary hypothesis of this clinical trial is that hydroxychloroquine, given in a clinically relevant dose to patients with T2DM who are taking metformin with or without other oral antihyperglycemic therapy, will reduce fasting glucose level and low density lipoprotein (LDL) . Secondly, we will test whether hydroxychloroquine will reduce insulin resistance with the primary effect being a reduction in hepatic glucose output. Tolerance to the specified dose of 400 mg daily in divided doses will be assessed in patients taking metformin +/- other anti-diabetic medications.

PRIMARY AND SECONDARY OUTCOMES

The primary outcome of this mechanistic clinical study is to determine whether hydroxychloroquine, compared with placebo, will reduce fasting blood glucose and/or LDL in patients with mild T2DM over a four-week treatment period.

Secondary (exploratory) outcomes are as follows:

1. To determine the effect of HCQ on insulin resistance
2. To determine the effect of HCQ on serum biomarkers of inflammation.

This clinical trial is based on the protocol for the hyperinsulinemic clamp that was used in Aim 2 of the ARCH-MS study. The basic plan of the study is to randomize otherwise healthy subjects with type 2 diabetes to hydroxychloroquine, 200 mg twice daily or placebo. All subjects will undergo fasting labs to include glucose and LDL at baseline, followed by a graded hyperinsulinemic clamp. The fasting glucose and LDL and graded hyperinsulinemic clamp will be repeated after 4 weeks of treatment along with other safety labs.

Primary and Secondary Endpoints. The primary endpoint of the protocol is reduction in fasting glucose and LDL. Secondary endpoints include insulin sensitivity determined by hyperinsulinemic euglycemic clamp and common serum biomarkers of inflammation.

PROTOCOL PLAN

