- 18. Need for daily OTC medications, or currently taking cimetidine or >1000 IU vitamin E daily and unwilling to reduce or discontinue vitamin E or discontinue cimetidine for the duration of the study. Patients taking more than 1000 IU vitamin E daily should reduce or discontinue the vitamin for 30 days before randomization.
- 19. Pregnant or lactating women, or women intending to become pregnant
- 20. Women not using adequate birth control (hormonal birth control is acceptable, also double barrier)
- 21. QTc >450 msec on screening ECG
- 22. Glucose-6-phosphate dehydrogenase (G6PD) deficiency

Study Plan and Procedures

Screening. Potential subjects will be interviewed, the protocol will be explained in detail, then risks and benefits of involvement will be discussed. Those subjects interested in participating will be given ample time to review the informed consent, to ask questions of any member of the study team, and will sign the informed consent prior to any study procedures being conducted. Subjects will have a complete history and physical examination (including measurement of blood pressure according to a standard protocol and determination of height, weight and waist size) performed by experienced personnel in the Washington University IRU or by the study coordinator. A POC A1c will be performed to determine whether the patient meets the inclusion criteria. If the A1c is 6.5-9%, blood will be drawn for G6PD, CBC and CMP; and an ECG will be performed and a pregnancy test for women of childbearing potential. This visit does not require fasting. Patients who have one or more exclusions will be informed of their test results but will not proceed further. If the patient meets the inclusion and exclusion criteria specified above at the screening visit, he or she will be scheduled for fasting labs and a hyperinsulinemic-euglycemic clamp, as depicted in the schedule of events.

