Study procedures. Patients who provide informed consent, and who meet the inclusion and exclusion criteria will return to the study site for fasting glucose (CMP) and lipids, repeat A1c (to be done in the Core Lab), then a hyperinsulinemic-euglycemic clamp and baseline serum samples for inflammatory biomarkers will be drawn. After the clamp procedure, patients will be randomized to receive either 200 mg HCQ or matching placebo twice daily. The patients will take the study medication until the final visit, for a total duration of 4-5 weeks. The fasting glucose (CMP), lipid profile, CBC and hyperinsulinemic, euglycemic clamp will be repeated at the final visit in 4-5 weeks. Additionally, blood for biomarker profile will be drawn at the last visit. Side effects and adverse events will be monitored during the study and medication compliance assessed at the last visit. The schedule of events is shown below.

META-HCQ Schedule of Events				
Procedure	Screening	Baseline Clamp	Follow-up Clamp	
	Week -2	Week 0	Week 4-5	
Informed consent	X			
H&P	X			
Vital signs	X	X	X	
ECG	X		X	
POC A1c	X			
CBC, CMP	X		X	
Pregnancy Test (urine) prn	X	X	X	
G6PD	X			
Lab A1c		X	X	
Fasting lipid profile, Biomarkers		X	X	
Fasting glucose		x	X	
Graded hyperinsulinemic clamp		x	X	
Randomize to HCQ, 200 mg bid vs placebo bid		x		
Dispense study drug		x		
Drug accountability, return			X	
Adverse events		X	X	

Subjects are advised to maintain current dietary and exercise habits. Weight, BP and HR are recorded throughout the protocol.

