Hyperinsulinemic-euglycemic clamps- Study patients will be asked to arrive fasting and without taking their oral anti-diabetic medications or the study medication. Two-step clamps will be performed according to a standard protocol routinely used in the Washington University IRU with hepatic glucose output determined using [6,6-²H] glucose (detected by mass spectrometry in our core facility). IV lines will be started and samples for fasting glucose, c-peptide, glucagon and insulin obtained. A stable isotope-labeled glucose prime (1 mmol/m) will be given at the beginning of a 150 minute baseline equilibration period, followed by a constant infusion (0.01 mmol/m²/min). After tracer equilibration, insulin will be infused in an exponentially decreasing manner until a rate of 8 mU/m²/min is achieved. The glucose will be clamped at 90 mg/dby altering the infusion rate of 20% dextrose based on glucose concentrations sampled from an arterialized hand vein (achieved by maintaining the hand in a heating box). The first step of the clamp will be carried out for two hours with a stable glucose infusion rate maintained for the final hour at the 8 mU/m²/min rate. Multiple blood samples are obtained at standardized times for determination of glucose kinetics. The second step will be carried out at 40 mU/m²/min in an analogous fashion. Potassium will be monitored during clamps and replaced appropriately. Glucose appearance rate (Ra) will be calculated from plasma tracer enrichments and rate of tracer infusion, endogenous glucose output will be calculated as Ra minus the glucose infusion

rate, and the glucose disposal rate will be calculated as glucose infusion rate plus endogenous glucose output. This visit takes 8-9 hours.

Blood tests. Most determinations will be performed by the Washington University Core Lab for Clinical Studies, a CLIA-certified facility that has served as the reference lab for landmark clinical trials including the Coronary Primary Prevention Trial and the CARE trial. The lab will measure A1c, CBC, CMP and lipid profiles including total cholesterol, HDL, triglycerides and calculated LDL at baseline and study end. Additional aliquots will be frozen for future studies of inflammatory biomarkers.

Sample Size Estimates and Statistical Analyses

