The primary endpoint for this experiment is fasting glucose and fasting LDL. Insulin sensitivity determined by clamp is an exploratory aim. Based on the results of Aim 2 of the ARCH study, we expect to show a difference from baseline in fasting glucose and LDL in 15 subjects per group (80% power and $\alpha=0.05$). We will therefore plan to study 15 subjects per group. We will compare differences between groups using unpaired two-tailed t tests. An interim analysis will be performed after the first 7 patients in each group have completed the study to check for significant differences or refine the sample size.

Anticipated Results, Alternative Approaches, Potential Problems and Benefits

The anticipated results of the study are that HCQ will reduce fasting glucose and will produce a small reduction in LDL. We also anticipate that HCQ will reduce glucose appearance, also known as hepatic glucose output. Based on our prior studies, no effect on blood pressure is expected. The major unknown in this study is whether HCQ at the clinically used dose of 200 mg bid will have the same effect as chloroquine. It is also not known whether HCQ will have the expected effect in the presence of metformin, since the drugs appear to have similar mechanisms of action. The LDL lowering effect of chloroquine was mild in the ARCH study, but not all patients were taking statins, and the mean LDL was higher than is commonly seen in patients with diabetes who are treated to lower LDL targets than non-diabetics. Therefore, the effect size of HCQ on LDL is unknown in this patient population. The results of this mechanistic study will be informative for the planning of future clinical trials of HCQ in persons with diabetes. The hyperinsulinemic clamp are considered to be the gold standard tests for mechanistic studies of the metabolic defects in diabetes, and thus do not have comparable alternatives.

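### Baseline information is under-used in a 15-per-group comparison: one fasting morning before treatment, no baseline covariate in the analysis, and a Week -2 blood draw that cannot contribute

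*Combined protocol and SAP*

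**What the plan says.** The protocol's endpoint paragraph states that "The primary endpoint of the protocol is reduction in fasting glucose and LDL", and the section on sample size and statistical analyses repeats that "The primary endpoint for this experiment is fasting glucose and fasting LDL". The sizing sentence reads "we expect to show a difference from baseline in fasting glucose and LDL in 15 subjects per group", at 80% power and alpha 0.05. The test is a two-sided unpaired t test between groups. No covariate is named, and the text does not say whether the change or the final value is compared.

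The measurements fall as follows:

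- **Week -2 (Screening):** "If the A1c is 6.5-9%, blood will be drawn for G6PD, CBC and CMP". The same paragraph says "This visit does not require fasting". No lipid profile is ordered.
- **Week 0 (Study procedures and Schedule of Events):** fasting glucose and lipids on the morning of the baseline clamp, before randomisation.
- **Week 4-5:** "The fasting glucose (CMP), lipid profile, CBC and hyperinsulinemic, euglycemic clamp will be repeated at the final visit in 4-5 weeks".

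No second baseline day is planned. The clamp paragraph has patients arrive fasting and without their oral anti-diabetic medications. The Screening paragraph sets no such condition.

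**The concern.** A single fasting value carries day-to-day variation. If change from baseline is compared, all of that variation at Week 0 enters the result. If final values are compared, the baseline is not used at all. Either way, a t test without a covariate leaves precision unused in a trial of 30 patients that states no effect size, no SD and no dropout allowance, and that calls the LDL effect size unknown in this population. Follow-up requires a second clamp visit of 8-9 hours, so precision gained from baseline data costs much less than precision gained from more patients.

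**Working it through.** **The plan's own figure.** The 15 per group cannot be reproduced, because no difference and no SD are given. It can only be inverted. By the normal approximation, the standardised difference detectable with 80% power at two-sided 0.05 is (1.960 + 0.842) × √(2/15) = 1.02. By the exact noncentral t it is 1.06. The comparison can therefore reliably detect only a difference of about one SD.

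**Assumptions.** Unit variance at each visit and a common correlation r between any two visits. The documents give no r, so 0.5, 0.7 and 0.9 are used as a range.

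**Step 1: adjust for Week 0 alone, with no extra blood.** The variance of the change is 2(1 − r). The residual variance after adjustment is 1 − r². With N = 30, k covariates inflate the expected variance of the treatment difference by (N − 3)/(N − 3 − k), which is 27/26 for one covariate.

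| r | Change score | Adjusted for Week 0 | Variance removed | After the lost degree of freedom |
|---|---|---|---|---|
| 0.5 | 1.00 | 0.75 | 25% | 22% |
| 0.7 | 0.60 | 0.51 | 15% | 12% |
| 0.9 | 0.20 | 0.19 | 5% | 1% |

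If the plan means final values, the unadjusted variance is 1. Adjustment then removes r² of it: 25%, 49% or 81% before the lost degree of freedom.

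**Step 2: add a fasting Week -2 value as a second covariate.** Let s be its correlation with follow-up, and keep r for the other two pairs. Then R² = (r² + s² − 2r²s)/(1 − r²). Example with r = 0.7 and s = 0.65: (0.49 + 0.4225 − 0.637)/0.51 = 0.540. The residual is 0.460, and the ratio to Step 1 is 0.460/0.51 = 0.90. The second degree of freedom multiplies each ratio by (27/25)/(27/26) = 1.04.

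| r | s = r | × 1.04 | s = r − 0.05 | × 1.04 | s = r − 0.10 | × 1.04 |
|---|---|---|---|---|---|---|
| 0.5 | 0.889 | 0.924 | 0.929 | 0.966 | 0.960 | 0.998 |
| 0.7 | 0.830 | 0.864 | 0.902 | 0.938 | 0.954 | 0.992 |
| 0.9 | 0.776 | 0.807 | 0.956 | 0.994 | 0.997 | 1.037 |

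The further gain after the lost degree of freedom is 8-19% with equal correlations and about 1-6% with s lower by 0.05. With s lower by 0.10 it lies between a 1% gain and a 4% loss.

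**Step 3: covariate or simple mean?** With s = r − 0.05, using the mean of the two baselines in a change score gives variance ratios of 0.80, 0.83 and 1.00 against the single-baseline change at r = 0.5, 0.7 and 0.9. Adjusting for that mean gives 0.93, 0.91 and 1.02 against Step 1. At r = 0.9 the mean gains nothing or loses. Separate covariates give 0.956 there, before the lost degree of freedom, because the model can down-weight the older value.

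**Both steps together.** Against a single-baseline change score, with s between r − 0.05 and r, the two covariates remove 9-33% of the variance before the two lost degrees of freedom. Multiplying the remaining 0.908 and 0.667 by 27/25 gives 0.98 and 0.72, so 2-28% after them.

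**The case against.** **A single baseline morning is a legitimate design choice.** This stands. Randomisation protects the comparison, and nothing in the plan is contradictory on this account. Without an SD or a within-subject variance, the documents cannot show how much the noise matters.

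**Most of the benefit needs no new measurement.** This largely stands at lower correlations. Step 1 uses data already planned, and under mild decay the Week -2 value adds only a few per cent.

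**The Week -2 value may not match Week 0.** This stands. The clamp visits specify a medication condition that Screening does not. A mismatch would lower the correlation with follow-up, which is a further reason against a simple mean.

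**Fasting would have to be requested before consent.** This stands as a practical limit. The Screening paragraph places the interview and the consent signature before any procedure and describes no separate earlier contact.

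**Stronger readings that a reader might infer.**

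- *A second baseline cuts the variance by a quarter, equal to 20 per group and about 90% power.* That holds only for a two-day mean in a change score, with equal correlations at all visits and no variation between patients in true change. If the variance of true change is up to twice the day-to-day variance, the cut falls to 12.5%. With a small decay at r = 0.9 it vanishes.
- *Information already collected is being thrown away.* For LDL nothing is, since no lipids are drawn at Week -2. The glucose in that CMP is not a fasting value.
- *Two same-morning glucose values at each clamp visit could be averaged.* The clamp paragraph says "IV lines will be started and samples for fasting glucose, c-peptide, glucagon and insulin obtained", but the documents do not establish that this is a different sample from the CMP glucose, and the schedule has one fasting-glucose row. A same-morning value would not average out day-to-day variation in any case.

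**Conclusion.** The point holds as a cheap gain in efficiency. The plan names no baseline covariate and has one fasting baseline morning, so it forgoes precision in a comparison that needs a difference of about 1.06 SD for 80% power. The dependable part is adjustment for Week 0. The Week -2 value is a modest addition whose worth depends on how well it correlates with follow-up. All percentages rest on assumed correlations and equal variances across visits, and none can be confirmed from the documents. It would be wrong to infer that the treatment comparison is biased, or that 15 per group has been shown to be too few. The sample size cannot be verified, which is a different matter. Follow-up is also a single morning, and its noise remains whatever is done at baseline.

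**What to change.** 1. **Sample Size Estimates and Statistical Analyses:** state that follow-up fasting glucose and follow-up LDL are each compared between groups with the Week 0 value of the same variable as a covariate. This also settles whether change or final value is analysed. Cost: a line of text and one degree of freedom.
2. **Screening and Schedule of Events:** add a lipid profile to the Week -2 draw, and invite but do not require fasting attendance, under wording approved by the ethics board. Cost: one lipid profile per A1c-eligible patient, and the burden of fasting for some who then fail the A1c check.
3. **Analysis of Week -2:** enter a fasting Week -2 value as a second covariate, not as part of a mean. Prespecify a rule, blind to treatment group, that keeps patients without it in the analysis. A missing-value indicator is one example. A complete-case model would drop patients from a trial of 30.
4. **Sampling conditions:** record fasting state and medication status at Week -2. The Screening and clamp paragraphs differ on oral anti-diabetic medication before sampling and must be reconciled before the two glucose values are treated as equivalent.

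If items 2 to 4 prove impractical, item 1 is worth making alone.

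### The planned t test names no outcome variable (change or final value) and makes no use of the baseline values already collected; a prespecified baseline-adjusted ANCOVA would settle both at almost no cost

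*Combined protocol and SAP*

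**What the plan says.** The section Sample Size Estimates and Statistical Analyses contains the full statistical plan. It defines the endpoint as follows: "The primary endpoint for this experiment is fasting glucose and fasting LDL". The sample size is justified by the statement that "we expect to show a difference from baseline in fasting glucose and LDL in 15 subjects per group", at 80% power and alpha 0.05. The analysis is then given in one sentence: "We will compare differences between groups using unpaired two-tailed t tests". No covariate or adjusted model appears there or elsewhere.

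The data needed for adjustment are in the design. Primary and Secondary Outcomes states: "All subjects will undergo fasting labs to include glucose and LDL at baseline". The Study procedures text puts these measurements before allocation: "After the clamp procedure, patients will be randomized to receive either 200 mg HCQ or matching placebo twice daily". The same measurements are repeated once, at the final visit in week 4-5.

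**The concern.** Two things are left open.

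- **The tested variable.** The analysis sentence does not say what is compared. The sample size sentence, with its reference to baseline, makes change the likelier reading, but it justifies a number and does not define an analysis variable. The endpoint wording does not settle the matter: one section calls the endpoint a reduction in fasting glucose and LDL, the other simply fasting glucose and LDL.
- **Baseline is not a covariate under either reading.** An unadjusted comparison is unbiased over randomizations but usually less precise than ANCOVA. In a given trial, part of any chance baseline imbalance carries into the estimate: (1 − ρ) times the imbalance for change scores and ρ times the imbalance for final values, where ρ is the baseline-to-final correlation.

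With 15 subjects per group and an LDL effect that the protocol itself calls unknown, precision available from data already collected is worth taking. Naming one model in advance also removes a choice that could otherwise be made after the results are seen.

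**Working it through.** **Inputs from the protocol.** n = 15 per group, two-sided α = 0.05, power 80%, unpaired t test (28 df), one baseline and one follow-up measurement.

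**Assumptions.** The documents give no mean difference, SD or correlation. I take equal SDs at baseline and follow-up (set to 1), normal data, no dropout, and one endpoint at α = 0.05. The correlation ρ is varied from 0 to 0.95.

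**Step 1: the plan's own figure.** Fifteen per group cannot be reproduced without an effect and an SD. Solving backwards, the noncentral t with 28 df and noncentrality d·√(15/2) reaches 80% power at d = 1.060 SD of the tested variable (1.02 by the normal approximation).

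**Step 2: ANCOVA against a t test on change.** The variance of a change score is 2(1 − ρ). The ANCOVA residual variance is 1 − ρ². Their ratio is (1 − ρ²)/[2(1 − ρ)] = (1 + ρ)/2. Allowing for chance baseline imbalance multiplies the ANCOVA variance by 1 + 1/(2n − 4) = 1 + 1/26 = 1.038. ANCOVA has 27 df, and its noncentrality is 1.060·√7.5 / √[1.038(1 + ρ)/2]. At ρ = 0.7, for example, this is 2.902/√(1.038 × 0.85) = 3.09, which gives 84.6% power.

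**Step 3: the t test on final values at the same effect.** The effect that gives the change-score test 80% power is 1.060·√[2(1 − ρ)] SDs of the final value. At ρ = 0.7 this is 1.060 × √0.6 = 0.82, which gives 58% power.

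| ρ | t test on change | ANCOVA | t test on final value |
|---|---|---|---|
| 0.3 | 80% | 92.6% | 91% |
| 0.5 | 80% | 88.7% | 80% |
| 0.7 | 80% | 84.6% | 58% |
| 0.8 | 80% | 82.5% | 43% |
| 0.9 | 80% | 80.4% | 24% |
| 0.95 | 80% | 79.4% | 14% |

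ANCOVA and the change-score test break even at ρ = 0.92. In the limit ρ = 1, ANCOVA has 78.4%, a loss of 1.6 points. Simulation (40,000 trials each) gave 92.5% for ANCOVA at ρ = 0.3 and 80.7% at 0.9.

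**Step 4: starting instead from 80% power on final values.** The variance ratio is now 1 − ρ², again multiplied by 1.038. ANCOVA has 78.4%, 82.1%, 88.7% and 97.0% at ρ = 0, 0.3, 0.5 and 0.7.

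**Step 5: chance imbalance.** The standard error of the baseline difference is √(2/15) = 0.365 SD. The probability that it exceeds 0.5 SD in either direction is P(|Z| > 0.5/0.365 = 1.37) = 17% per endpoint. An imbalance of that size shifts a change-score estimate by 0.5(1 − ρ): 0.35, 0.25, 0.15, 0.10 and 0.05 SD at ρ = 0.3, 0.5, 0.7, 0.8 and 0.9.

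**Step 6: the open choice under the null.** If success were declared when either the change or the final-value test was significant, simulation gives about 9% to 10% false positives per endpoint at ρ from 0.3 to 0.9, against a nominal 5%. Nothing suggests that this is intended; the text merely does not exclude it.

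**The case against.** The strongest reply is that this is a preference between valid analyses in a small mechanistic study. The t test has no bias and the correct error rate, and chance imbalance is already reflected in its standard error: a 0.5 SD imbalance moves the change-score estimate by 0.8 standard errors at ρ = 0.3 (0.35/0.43) and 0.3 at ρ = 0.9 (0.05/0.16). That is right, and it is why the point is not graded as an error.

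Further points, and what stands of each:

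- **Change is the natural reading, and adding that one word would close the wording gap.** True. The low final-value powers in the table arise only under the less likely reading. But naming change would forgo the gain at low and moderate correlations.
- **The 13-point figure is the favourable end of an assumed range.** True. At ρ = 0.3 most of it reflects the inefficiency of change scores, since a final-value t test already has 91%. But ρ is unknown, and ANCOVA stays close to or above the better of the two t tests at every value.
- **The 80% starting point cannot be verified.** True. If 15 per group came from a within-group paired calculation (standardized change 0.78), the same standardized effect would give the between-group t test about 54%. The powers above would then differ, but the variance ratio in step 2 would not.
- **The interim analysis after 7 per group is less forgiving.** True. At the same effect the change-score test has 45% power there. ANCOVA breaks even near ρ = 0.8 and falls to 41% as ρ approaches 1, a loss of about 4 points. The cost is still small, but the plan should say which model applies at that look.
- **No calculation supports extending the model to the clamp measures.** True. That part is a matter of consistency for exploratory outcomes.

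**Conclusion.** The concern holds. The plan does not name the tested variable and leaves unused a baseline measurement taken in every subject. The t test itself is valid. Taking 80% power on change scores at face value, prespecified ANCOVA gains about 13 points at a correlation of 0.3, 5 at 0.7 and essentially none at 0.9, with a worst case of minus 1.6 points at 15 per group. These figures rest on assumed correlations, equal SDs at the two visits, one endpoint and no dropout. The case for naming one model in advance does not depend on any of them. The change should be made, but the trial is not invalid without it.

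**What to change.** Replace the analysis sentence with wording such as: *Each primary endpoint will be analysed by ANCOVA of the week 4-5 value on treatment group, with the baseline value of that variable as covariate (two-sided). The adjusted mean difference between groups will be reported with its 95% confidence interval. An unpaired t test on change from baseline will be a sensitivity analysis.*

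State whether the same model applies at the interim analysis, and preferably use it for the exploratory clamp measures as well.

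The cost is one sentence and one degree of freedom, with no new visit, sample or subject. At the final analysis the power loss is at most about 2 points, and only if the correlation is extreme: near 1 compared with change scores, or near 0 compared with final values. At 7 per group it could reach about 4 points compared with change scores.
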